Participating subjects will receive treatment using an FDA-approved f1927 laser, currently considered a standard of care treatment for melasma and hyperpigmentation in Fitzpatrick Skin Phototypes I-VI. Subjects will undergo treatments over the entire face. Subjects' response to effects of the f1927 treatment will be quantified based on evaluation of standard and clinical photography and H2 3D Imaging System images taken pre- and post-procedure. These photos will be identifiable full-face photos, and subjects will be adequately informed and consent of such. In addition to the two standard care photographic assessments, subjects will also have photos taken using the VISIA and/or VISIA-CR (Canfield Scientific, Fairfield, NJ). A quantitative assessment of the effects of treatment will be performed using VISIA and/or VISIA-CR at 1-month and 3-months post-treatments. Additional assessment will be provided by use of the Skin Hyperpigmentation Index (<https://shi.skinimageanalysis.com/> - Inselspital, Freiburgstrasse, Switzerland) [12-15] a web-based software used to quantify hyperpigmentation. Changes in the Skin Hyperpigmentation Index over time will be used to objectively report on subjects' treatment response.

From these procedures, the improvement in diffuse pigmentary changes can be evaluated in comparison to pre-treatment assessments.

Primary Endpoints

1. Quantifying Improvement in overall facial hyperpigmentation in response to laser treatment, by measuring pigmentation at baseline and follow-up visits post-treatment using the VISIA and/or VISIA-CR
2. Changes in Skin Hyperpigmentation Index (SHI) Scores from Baseline to post-treatment visits..

Secondary Endpoints

1. Monitoring incidence, severity, and relatedness of adverse events throughout the study
2. Monitoring the efficacy of pre- and post-treatment regimens with tretinoin and hydroquinone
3. Monitor the efficacy of the pre- and post-treatments with Clobetasol and ice.

Standard of Care Treatment Device

Proprietary Name	Device Description	Regulatory Information
Sciton MOXI	Aesthetic device that utilizes a fractionated laser to initiate resurfacing for the treatment of dyspigmentation and healing of photoaged skin.	Class II 510(K) Number: N/A Regulation Number: 878.4810

Study Population, Screening, and Enrollment

Study Population

The study population in question includes patients ages 18-75 with Fitzpatrick Skin Phototypes V and VI.

Subject Enrollment

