Following the final treatment, patients should continue to take their 4% Hydroquinone and Tretinoin 0.1% cream as prescribed through the remainder of the study.

Part 2:

Subjects will be asked to refrain from using any topical prescription medications on their face for at least 4 weeks prior to treatments commencing. Subjects who participated in Part 1 will be eligible for Part 2 if they agree to complete the topical regimen washout period and agree to refrain from any other treatments for the remainder of their trial participation.

Pre-Treatment Instructions:

Subjects will be asked to wash off all skincare products at least 30 minutes prior to each scheduled clinic visit using a cleanser of your choice. If a subject arrives having not removed skincare products, she or he will be required to remove the residual product at the clinic and wait at least 20 minutes prior to procedures.

Post-treatment Instructions:

Immediately post-treatment Clobetasol Propionate 0.05% and ice will be applied to the treated areas for 15-20 minutes. The subject will be instructed to re-apply Clobetasol Propionate 0.05% twice a day and ice the treated area for 15 minutes up to four times a day for four days.

Blistering, bleeding, oozing, strong pain, swelling persisting for more than 24 hours, or signs of infection (e.g., pus, drainage, fever) are cause for immediate concern and you should contact the investigator and/or his designee to be evaluated and potentially treated at no cost to the subject.

Subjects will be asked to avoid extended periods of sun exposure and all use of tanning beds for the duration of the study. Extra care should be taken to wear protective clothing and avoid sun exposure from 10 AM to 4 PM.

Subjects will be encouraged to consistently use face wash, moisturizer, and sunscreen of their choosing. Subjects will be asked to refrain from using any new anti-aging, acne, and acne scar products or devices and beginning the use of any new skincare products or devices other than the assigned test material for the duration of the study.

Study Design

Study Timeline and Procedures

Study Procedure		Part 1						Part 2					
		Screening	Treatments			Follow Up		Screening	Treatments			Follow Up	

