Subjects will be instructed to adopt neutral, non-smiling expressions for each photograph. Images will be taken of each applicable subject with diffuse pigmentation of the face using the Vectra H2 3D Imaging System at Baseline, 1-month post-treatment and 3-months post-treatment. Each subject will have a total of 3 photos taken (right side, left side and center view).

VISIA and/or VISIA-CR (Research Purposes)

Subjects will be instructed to adopt neutral, non-smiling expressions with their eyes gently closed for each photograph. Images will be taken of each applicable subject using the VISIA and/or VISIA-CR at Baseline, 1-month post-treatment and 3-months post-treatment. Subjects will be carefully positioned for each photograph, directly facing the camera for the center view, and turned at a 45° angle for right and left side views. The scan is objectively able to quantify brown spots for assessment and comparison.

Hyperpigmentation Assessment

Skin Hyperpigmentation Index (SHI) (Research Purposes)

The SHI will be calculated using de-identified, cropped images from patient's unaffected skin and patient's hyperpigmented lesions. Images uploaded will be selected from the clinical or lab-based photography the patient has taken at their screening/baseline visit and their 1-month and 3-month follow-up visits. Care will be taken to compare lesions using the same lighting and angles to reduce confounders. The software is able to calculate the relative contributions of pigmentation of each pixel to create a score, and a coefficient is then derived from comparing Pigmentation Scores of the Area with hyperpigmentation versus the Reference Point. This will be used to quantify the change in pigmentation between treatments.

Statistical Methods of Analysis

The per-protocol (PP) population will be the primary population for all statistical analyses. The PP population will include all subjects who received treatment and completed the study in general accordance with the protocol. Only the data of completing subjects will be analyzed.

This study will include descriptive statistics and change from baseline analysis.

The primary outcome of effectiveness will be a paired comparison of baseline to all applicable post-baseline time points for hyperpigmentation and melasma severity using data obtained from VISIA and/or VISIA-CR and the Skin Hyperpigmentation Index results.

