The risks of photography and imaging are the same for all three imaging modalities used: close-range clinical photography (Nikon D7200), 3D Photography (Vectra H2), and the VISIA and/or VISIA-CR. Photographs include a risk of identification, as these will be full face photos. Privacy will be protected to the greatest extent possible. Photos will only be identified by unique subject identification number that contains no personal identifying information. All photos will be stored on a password secure drive, with only access by research personnel. For research purposes, photos may be used in scientific publications.

Adverse Events

At each visit, a member of the research team will question the subject about adverse events using an open-ended question. If a potential adverse event is reported by the subject or identified during examination, directed questioning and examination will be performed when appropriate. At this time, the following will be performed:

1. Obtain a complete history of the event in question as well as conduct an examination of the subject and determine if the reported event qualifies as an Adverse Event (AE). If the event is determined to be an AE, an AE case report form and Event Follow-up (EF) visit case report form must be completed. One AE case report form should be used to track the history of an individual AE throughout the period of the study.
2. Collect an updated medical and surgical history along with recording of concomitant medications or treatments.
3. Take photographs of the subject with attention to the area in question.
4. Render treatment for the event, if any, as determined by the medical judgement of the Investigator.

Photographs will be taken to document any AEs if possible.

For the duration of the study, medical assistance will be provided to the subject for study-related problems at no expense, if in the opinion of the Investigator, the reaction was caused by MOXI treatments. Should a subject choose to seek their own medical treatment, no reimbursement will be offered.

When an AE persists at the end of the study, the Investigator will ensure a follow-up of the subject until the Investigator believes that the event is satisfactorily resolved.

Subject Safety and Data Monitoring

Research Standards and Good Clinical Practice

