The conduct of this study will follow all applicable guidelines for the protection of human subjects for research as outlined in 21 CFR 50, in accordance with the accepted standards for Good Clinical Practice (GCP), International Conference on Harmonization (ICH), and the standard practices of UT Southwestern.

Data Monitoring

For this protocol, which involves the use of a non-significant risk device, the Investigator will monitor accrual, subject experience, attrition, patterns of adverse events and/or unexpected adverse events, any protocol deviations, or violations any changes in the risk/benefit analysis.

Subjects will be asked about any adverse events throughout the study. Subjects will be asked to contact the Investigator if adverse events develop between visits. If necessary, an unscheduled visit will be arranged so that the Investigator can clinically evaluate and photograph these findings.

Procedures to Maintain Confidentiality

All study records and information will be identified by the subject number. All subject identifiers will be removed from all documents. The link between subject name and study ID number will be kept in separate password-protected files. Documents containing identifying information will be kept in locked files in the research staffs' locked office. All electronic study data will be password protected with access limited to members of the research team. No direct identifying information will be shared with any outside entities. Electronic data (electronic data entry - Case Report Forms) will be password protected.

Photographs of subject's faces will be taken at enrollment, treatment, and follow-up visits. These photographs will be identified by subject numbers. Subject confidentiality will be protected to the greatest extent possible

This study will be performed in accordance with Health Insurance Portability and Accountability Act. These guidelines will be followed specifically with regard to the privacy and confidentiality of patient care and study records. Personnel associated with Investigator's office, the U.S. Food and Drug Administration (FDA) and the governing Institutional Review Board, have the right to review the data, including photographs, collected during this study.

References

1. Kaufman, B.P., T. Aman, and A.F. Alexis, *Postinflammatory Hyperpigmentation: Epidemiology, Clinical Presentation, Pathogenesis and Treatment*. Am J Clin Dermatol, 2018. **19**(4): p. 489-503.

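### Analysis is limited to per-protocol completers, with no safety or all-treated population: read literally, treated subjects who stop leave the adverse-event summaries, and their usable Day 90 images are discarded

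*Combined protocol and SAP*

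**What the plan says.** Three statements in Statistical Methods of Analysis set the rule:

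- "The per-protocol (PP) population will be the primary population for all statistical analyses".
- That set consists of "all subjects who received treatment and completed the study in general accordance with the protocol". Neither completion nor general accordance is given criteria.
- "Only the data of completing subjects will be analyzed".

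No safety, all-treated or intention-to-treat set is named anywhere, and there is no missing-data rule. The section describes no separate adverse-event analysis.

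Other sections bear on the same point:

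- The first secondary endpoint is "Monitoring incidence, severity, and relatedness of adverse events throughout the study".
- Under Adverse Events, subjects are asked about events at each visit. Follow-up goes beyond the study if needed: "When an AE persists at the end of the study, the Investigator will ensure a follow-up of the subject".
- Under Data Monitoring, "the Investigator will monitor accrual, subject experience, attrition, patterns of adverse events".
- Under Assessments, "Images will be taken of each applicable subject using the VISIA and/or VISIA-CR at Baseline, 1-month post-treatment and 3-months post-treatment". The post-treatment visits are Day 90 and Day 150.
- Under Subject Instructions, Part 2, "Subjects who participated in Part 1 will be eligible for Part 2 if they agree to complete the topical regimen washout period".

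**The concern.** The objective includes preventing iatrogenic dyspigmentation and scarring in skin types V and VI. The subjects most informative about that harm may be those who stop because of it. The plan collects their events, then applies a general rule that leaves them out of anything analysed.

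For efficacy, the primary outcome compares baseline with every applicable later time point. A subject with a Day 90 image and no Day 150 visit supplies a valid Day 90 pair, but is not a completer on the natural reading.

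Two ambiguities add to this. Without criteria for general accordance, exclusions in a non-blinded study could be settled after results are seen. And because completion is not defined by Part, the text does not say whether leaving during Part 2 removes a finished Part 1 record.

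The direction of bias depends on why people stop, which the documents do not address. If subjects who darken, scar or fail to respond stop more often, harm is understated and improvement overstated. The free care offered for device-related reactions could work the other way.

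**Working it through.** The plan states no dropout rate, SD, effect size or power, so there is no figure to reproduce. The only input taken from it is the sample size of about 20 (Overview of Clinical Study). Everything else below is assumed, including that all 20 are treated and counted in one analysis.

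**1. Adverse-event denominator.** Suppose *d* of 20 treated subjects stop with dyspigmentation and no completer has it. The completer report is 0/(20 − *d*), with exact upper 95% limit 1 − 0.025^(1/(20 − *d*)). For *d* = 2 this is 1 − 0.025^(1/18) = 18.5%. The all-treated report is *d*/20 with Clopper-Pearson limits.

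| Stopped with event | Completers (upper limit) | All treated (95% CI) |
|---|---|---|
| 1 | 0/19 (17.6%) | 1/20 = 5% (0.1–24.9%) |
| 2 | 0/18 (18.5%) | 2/20 = 10% (1.2–31.7%) |
| 3 | 0/17 (19.5%) | 3/20 = 15% (3.2–37.9%) |
| 4 | 0/16 (20.6%) | 4/20 = 20% (5.7–43.7%) |
| 5 | 0/15 (21.8%) | 5/20 = 25% (8.7–49.1%) |

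This is the extreme case. In a milder one, 3 of 20 have an event (15%) and 2 stop. If both who stop had the event, completers show 1/18 = 5.6%. If neither did, they show 3/18 = 16.7%.

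**2. Bias in the mean change.** Assume no true change, normally distributed change scores, and that the *d* subjects with the highest propensity to stop leave. Propensity has correlation *r* with poor response. The expected spurious improvement, in SDs of the change, is

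*r* × (sum of the *d* largest expected normal order statistics for n = 20) / (20 − *d*).

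The five largest are 1.867, 1.408, 1.131, 0.921 and 0.745. For *d* = 4 the first four sum to 5.327, and 5.327/16 = 0.333. At *r* = 0.5 the bias is 0.5 × 0.333 = 0.17 SD.

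| *d* | *r* = 0 | *r* = 0.3 | *r* = 0.5 | *r* = 0.8 |
|---|---|---|---|---|
| 1 | 0 | 0.03 | 0.05 | 0.08 |
| 2 | 0 | 0.05 | 0.09 | 0.15 |
| 4 | 0 | 0.10 | 0.17 | 0.27 |
| 5 | 0 | 0.12 | 0.20 | 0.32 |

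A simulation of 100,000 trials gives the same values. At *d* = 4, *r* = 0.5, a single paired t-test declares false benefit in 10.4% of trials against a nominal 2.5%. The plan tests by ANOVA and then pairwise comparisons, so that is not the plan's own error rate.

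**3. What using all available visits recovers.** Take *d* = 4, *r* = 0.5 with the Day 90 change, and between-visit correlation 0.7 (40,000 simulated trials). Completers-only bias is 0.17 SD at Day 90 and 0.12 SD at Day 150, in line with 0.7 × 0.166 = 0.12.

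- If the four stop after Day 90, a likelihood estimate using all available images brings both biases to 0.00. Here stopping depends on an observed value, which is the missing-at-random condition.
- If the four stop before Day 90, both biases are unchanged. Assigning them no change scales the Day 90 bias by 16/20: 0.166 × 0.8 = 0.13 SD.

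**4. Precision.** The 95% half-width for a mean change is t(0.975, n − 1)/√n SDs: 0.468 with n = 20 and 0.533 with n = 16. This is the Day 90 cost of dropping four usable images even when stopping is unrelated to outcome.

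**The case against.** The plan contains no adverse-event analysis, so nobody is expressly removed from one. The statistics section deals only with image scores; adverse events are collected, photographed, followed and reviewed elsewhere without restriction to completers. This stands as far as it goes: the effect on adverse-event reporting comes from reading a general rule literally. But collection and oversight do not supply a denominator, and the only population rule in the plan excludes these subjects.

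The safety table is a worst case, and the protocol lists pigmentary change and scarring as rare. For 1 to 4 stopped subjects the completers' upper limit still reaches the all-treated rate. For reactions expected in nearly everyone, such as erythema at 99%, incidence would barely move. All of that is fair, and the figures are not a forecast. An interval that covers the rate still accompanies a reported 0% when events occurred.

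Completion is undefined, and reporting the number of observations at each time point is compatible with varying numbers by visit. So the loss of Day 90 images rests on the natural reading rather than an explicit statement. The wording still needs to settle it.

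Finally, a mixed model and imputation may seem heavy for an uncontrolled pilot, and they do not recover early stoppers. Both points stand. The essential correction is the two populations; the rest is support.

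**Conclusion.** The concern holds and should be corrected before analysis. The plan states a completers-only rule and provides no population that covers treated subjects who stop. Followed as written, it omits them from a stated secondary endpoint and, if completion requires Day 150, discards valid Day 90 pairs that the primary comparison calls for.

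The size is unknown because non-completion is not given. With 1 to 5 of 20 stopping, the illustrations run from no bias to an all-treated event rate of 25% reported as 0%, and to a spurious improvement of 0.32 SD. The upper ends require stopping to be strongly tied to harm or poor response. With stopping unrelated to outcome, the cost is precision only.

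**What to change.** Replace the completers-only wording with the following.

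1. **Safety.** Report adverse events in all subjects who received at least one laser session in that Part, by Part, with exact 95% intervals. List separately events in subjects who started the Part 1 topicals but never reached laser.
2. **Efficacy.** Include all treated subjects with a baseline and at least one post-treatment image, using every available visit, for example in a repeated-measures mixed model. Keep completers as a sensitivity analysis, with completion defined for each Part and exclusions fixed before images are scored.
3. **Non-completion.** Report numbers and reasons by Part and by timing: before Day 90, or between Day 90 and Day 150.
4. **No post-treatment image.** State how many such subjects there are and that the efficacy estimate does not cover them. Show a sensitivity analysis assuming no change and, as a harsher case, the worst change observed.

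These are changes to the analysis plan. The one possible addition to data collection is a recorded reason for stopping, which the documents do not explicitly provide for. The mixed model brings a missing-at-random assumption, and estimates may become slightly less favourable.

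Optionally, add an imaging session at early termination. It is the only item that would supply the missing outcome for subjects who stop before Day 90. The cost is one extra visit per such subject, about 30 minutes if similar to a planned follow-up visit.

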A descriptive statistical summary will be provided via the VISIA and/or VISIA-CR. The descriptive statistical summary includes the number of observations (n), mean, median, and standard deviation (SD), minimum (MIN) and maximum (MAX) values at all applicable time points.

A Skin Hyperpigmentation Index is derived automatically using the SHI plug-in. The SHI ranges from 1 (no hyperpigmentation) to 4 (maximum hyperpigmentation) and is a ratio between the Pigmentation Scores of Areas with Hyperpigmentation versus Pigmentation Score of the Reference Point.

The following will be calculated and reported for each evaluation parameter at the applicable post-baseline time point(s):

$$\text{Percent Mean Change from Baseline} = \frac{(\text{Visit Mean Score} - \text{Baseline Mean Score}) \times 100}{\text{Baseline Mean Score}}$$

For each new measurement set we will conduct a repeated measures of analysis of variance (ANOVA) to detect difference between sample distributions. If differences are detected, we will subsequently evaluate specific pairwise comparisons among the post-treatment visit times using a paired T-test or Wilcoxon signed-rank tests. All statistical tests will have a significance level $\alpha=0.05$ (i.e., $p<0.05$). P-values will be reported to 3 decimal places (0.000).

Potential Risks

Standard of Care Risks

Pre-Treatment: Hydroquinone (Rare)

Hydroquinone is a known and effective treatment for hyperpigmentation disorders and is particularly considered to be the standard of care for dermatologic treatment of unwanted hyperpigmentation. Reported adverse effects of hydroquinone administration are uncommon and include short-term cutaneous side effects like irritant contact dermatitis or, with excessive or long-term use or misuse, exogenous ochronosis. Additionally reported side effects include abnormal skin re-pigmentation in continually sun-exposed areas, or trimethylaminuria with chronic use.

Pre-Treatment: Topical Tretinoin (Rare)

Side effects of topical tretinoin are rare and include stinging of the skin, local dryness, hypopigmentation, application site reactions like erythema, irritation, or exfoliation, or, most rare, contact dermatitis or long-term skin changes.

Treatment: Non-Ablative Laser Facial Resurfacing (Rare)

Blistering, burning, scaling and infection (Rare)

A crust, blister or superficial wound can occur in the treatment area. The risk of infection will be minimized by proper wound care.

Bruising (Rare)

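### The pairwise tests in the analysis section omit baseline, so as worded they do not test the primary outcome

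*Combined protocol and SAP*

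**What the plan says.** The Statistical Methods of Analysis section states the target clearly: "The primary outcome of effectiveness will be a paired comparison of baseline to all applicable post-baseline time points". Both items under Primary Endpoints agree with it. The VISIA endpoint is to be obtained "by measuring pigmentation at baseline and follow-up visits post-treatment using the VISIA and/or VISIA-CR", and the second endpoint is "Changes in Skin Hyperpigmentation Index (SHI) Scores from Baseline to post-treatment visits". The Clinical Treatment and Assessments section adds that "the improvement in diffuse pigmentary changes can be evaluated in comparison to pre-treatment assessments".

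The tests come later in the Statistical Methods of Analysis section. A repeated-measures ANOVA is run for each set of measurements, without a list of the visits that enter it. If it detects a difference, "we will subsequently evaluate specific pairwise comparisons among the post-treatment visit times using a paired T-test or Wilcoxon signed-rank tests". The section also defines a percent mean change from baseline, with no test or interval attached. Every test uses alpha 0.05.

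The imaging times are set out under Assessments. For VISIA: "Images will be taken of each applicable subject using the VISIA and/or VISIA-CR at Baseline, 1-month post-treatment and 3-months post-treatment". For the SHI, images come from "their screening/baseline visit and their 1-month and 3-month follow-up visits". In both Parts, the treatment-visit procedures limit imaging to the time before the first treatment, so no outcome images are taken at Day 30 or Day 60.

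**The concern.** The sentence that names the paired tests and the sentence that defines the primary outcome point to different comparisons. An analyst who follows the testing sentence would detect a difference over time and then test only whether the two follow-up visits differ. That is a reasonable durability question, so the wording does not read as an obvious slip that everyone would correct in the same way.

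The study has no control group, so change from baseline is its main evidence of efficacy. If the laser works equally well at both follow-up visits, the named test will usually be non-significant and could be misread as no effect. If the benefit fades, the test may be significant and could be misread as improvement. An analyst who instead follows the primary-outcome sentence must choose the test, and decide whether the ANOVA gate applies, after the data are in.

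**Working it through.** The plan states no power or sample-size calculation, so there is no figure to reproduce. The main check is a count of comparisons, and the arithmetic after it only illustrates the consequence.

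**Which pairs does the wording cover?** The analysed time points in each Part are baseline, Day 90 (1 month) and Day 150 (3 months). Three time points give three pairs:

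| Pair | Needed for the primary outcome | Covered by the pairwise sentence |
|---|---|---|
| Baseline vs Day 90 | Yes | No |
| Baseline vs Day 150 | Yes | No |
| Day 90 vs Day 150 | No | Yes |

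An image taken just before the first treatment is still pre-treatment, so it does not add a pair. For subjects who take part in both Parts, cross-Part pairs of follow-up visits would also leave out baseline.

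**Does anything else in the section test change from baseline by visit?** The percent mean change is a ratio of group means with no test. The ANOVA, even with baseline as a level, is an omnibus test that shows neither the direction of a change nor the visit at which it occurred.

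**What is the consequence in numbers?** The protocol gives about 20 subjects and alpha 0.05. The following are assumptions: two-sided tests, 20 or 12 completers, and true differences of 0.8, 0.5 or 0.4 SD of the paired difference. Paired t-test power comes from the noncentral t distribution with n − 1 df and noncentrality d√n.

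- n = 20, d = 0.8: noncentrality 0.8 × 4.472 = 3.58, power 92.4%.
- n = 20, d = 0.5: 0.5 × 4.472 = 2.24, power 56.5%.
- n = 20, d = 0.4: 0.4 × 4.472 = 1.79, power 39.7%.
- n = 12, d = 0.8: 0.8 × 3.464 = 2.77, power 71.4%.

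With equal variances and correlations across visits, these translate as follows for Day 90 vs Day 150 at n = 20, before any ANOVA gate:

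- Equal improvement at both visits: true difference 0, rejection rate 5.0% by construction.
- Half of a 0.8 SD benefit lost by Day 150: difference 0.4 SD, 39.7%.
- All of it lost: difference 0.8 SD, 92.4%.

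**With the ANOVA gate.** Simulation of 100,000 trials per scenario used three visits including baseline, multivariate normal data, visit correlation 0.6, equal improvement at both follow-up visits, and F on 2 and 2(n − 1) df:

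| n, improvement | ANOVA significant | Each baseline contrast, gated | Day 90 vs Day 150, gated |
|---|---|---|---|
| 20, 0.8 SD | 95.4% | 91.1% | 5.1% |
| 12, 0.8 SD | 76.6% | 66.2% | 4.9% |
| 20, 0.5 SD | 59.7% | 49.1% | 4.8% |

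A separate simulation of 8,000 trials per setting agrees. At correlation 0.5 the SD of a paired difference is √(2 × (1 − 0.5)) = 1 visit SD, so the scales match. At n = 20 it gave gated baseline rates of 90.9% (0.8 SD) and 49.5% (0.5 SD), with 4.8% and 4.7% for Day 90 vs Day 150.

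**Precision of the mean paired change.** The 95% CI half-width is t(0.975, n − 1)/√n in SD units: 2.093/4.472 = 0.468 at n = 20, and 2.201/3.464 = 0.635 at n = 12.

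**The case against.** The best reply is that the baseline comparison is already in the plan. The same section announces an analysis of change from baseline, defines the primary outcome as a paired comparison with baseline, and then names paired tests. Read as a whole, one sentence supplies the contrast and the other supplies the method. The structure supports this. Without baseline, each Part would have two levels, the ANOVA would be equivalent to a paired t-test, and follow-up pairwise tests would be redundant. The percent mean change also shows direction and size at each visit. On this view the harm arises only if the analyst ignores the stated primary outcome, in a pilot of about 20 subjects.

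Much of this stands as evidence of intent: loose wording is more likely than a deliberate plan to test durability alone. But it does not supply the missing test. The ANOVA levels are inferred and not stated, the omnibus result locates nothing, and the percent change is descriptive. Pilot status does not settle the matter either, because the plan has chosen to test hypotheses at 0.05.

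Two narrower points also stand. The power figures rest on assumed effects and measure no actual harm. Reporting intervals whatever the ANOVA shows goes beyond what the wording correction strictly needs.

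**Conclusion.** The concern holds. The testing sentence, followed literally, covers one of the three pairs in each Part and neither of the two that make up the primary outcome. It is an inconsistency within one section, probably from loose wording, and it should be corrected before analysis.

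This conclusion rests on the text and the imaging schedule alone. The illustration depends on the assumed effects, completer numbers and normality. Under equal improvement the named pair rejects at about 5% and carries no information on efficacy, while the omitted baseline contrasts would have 56.5% to 92.4% power across the scenarios shown (49.1% to 91.1% behind the ANOVA gate).

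**What to change.** Amend the Statistical Methods of Analysis section as follows.

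1. State that baseline, Day 90 and Day 150 are the levels of the repeated-measures ANOVA, separately for each measure and each Part.
2. Replace the pairwise wording with comparisons of Day 90 against baseline and Day 150 against baseline, for each measure and each Part. List Day 90 against Day 150 as secondary.
3. Report the mean paired change from baseline with its 95% CI at each follow-up visit, whatever the ANOVA result.

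The same edit is a convenient place to settle two related matters. One is which image counts as baseline, since imaging is described both at screening and before the first treatment. The other is how the two baseline contrasts share alpha: unadjusted and independent, their family error rate is 1 − 0.95² = 0.0975, and a Bonferroni split would be 0.05/2 = 0.025 each.

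The cost is two or three sentences of text for the three numbered changes. No new data, visits or subjects are needed.
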